Design Features	
 • This is a phase 1, double-blind (sponsor-unblind), active control, and randomized study. • The study will consist of a screening period, an oral lead-in (OLI) phase, a wash-out phase, an injection phase, and a follow-up phase: 
 ○ A 30-day Screening Period ○ A 28-day OLI phase, CAB 30 mg once daily (QD) with sparse PK sampling through Day 29 ○ A 7 to 14-day Washout Period (starting on Day 29) ○ An Injection Phase 
 ○ up to Week 8 (Injection 2 Day 28) in Part 1 Cohorts 1, 2, 3, 4 and 4b ○ up to Week 4 (Injection Day 28) in Part 1 Cohort 4h and ○ up to Week 24 (Injection 2 Week 12) in Part 2 Cohorts 5 and 6 (if conducted) ○ A 52-week Follow-up Phase post last injection or until CAB is no longer quantifiable (if this occurs prior to Week 52) • Part 1 
 ○ Twenty participants recruited to Cohort 1 first, then to Cohort 2 and followed by Cohort 3. Participants will be randomized (9:1 Active vs Active Control [AC]) according to a pre-generated randomization schedules in each cohort. ○ Cohorts 1-3 are required and will be enrolled sequentially. ○ Cohort 4 is optional and will be based on an interim review of the safety and tolerability data from Cohorts 1-3 and PK data through Week 4 from Cohorts 1-2. ○ Cohort 4b: Two subcutaneous injections of CAB 400 mg/mL formulation 4-weeks apart (each 300 mg) CCI XXXXXXXXXXXXXXXXXXXX XXXXXXXXXXXX Participants (n=24) will be randomized in equal numbers according to a pre-generated randomization schedule to one of two sequences (i.e. 12 per sequence) of two treatments to be administered along with Injection 1 and Injection 2, respectively ○ Cohort 4h: One subcutaneous injection in the abdomen with rHuPH20 followed by CAB 400 mg/mL formulation (400 mg) or CAB 200 mg/mL (400 mg). Instructions regarding drug preparation and administration are provided in the pharmacy manual. Participants will be randomized to receive 5000 U of rHuPH20 followed by either CAB 200 mg/mL or CAB 400 mg/mL formulations at a dose of 400 mg (2 mL and 1 mL, respectively). Four sentinel participants (two each administered CAB 200 mg/mL and CAB400 mg/mL formulations) will be followed clinically for 10 days after dose administration and if there are no significant safety concerns upon a 10-day review of safety data, the remaining 16 participants will be dosed with rHuPH20 plus either CAB 200 mg/mL or CAB 400 mg/mL. • Part 2 
 ○ Cohort 5 in Part 2 will commence once C_τ and plasma AUC_{0-t} up to and including Week 8 following Injection 1 (i.e., Week 4 following Injection 2 [Injection 2 Day 28/Week 4 follow-up]) from all participants in Cohort 1, and available safety and tolerability collected from each Cohorts 1-3 are reviewed and compared to historical PK data of the CAB 200 mg/mL formulation from Phase 2/3 program.

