4. ANALYSIS POPULATIONS

For the Cohort 1-5 preliminary interim analysis, displays will exclude Cohort 4b data from participants who have received injection 1 but have not yet completed Injection 2 Day 1 or Follow-up Week 4 by the data analysis cut-off. Cohort 4b will remain blinded to the randomized mitigation treatments **CCI** and results will not be presented by mitigation group for the interim analysis.

Population	Definition / Criteria	Analyses Evaluated
Screened	All participants who were screened for eligibility.	
 Study Population
Enrolled	
All participants who passed screening and entered the study.
 
Note: screening failures (who never passed screening even if rescreened) and participants screened but never enrolled into the study are excluded from the Enrolled population as they did not enter the study.
	
 Study Population
Randomized	All participants who were randomly assigned to treatment in the study.	
 Study Population
Safety	
All participants who received at least one dose of study treatment (oral or injection).
 
This population will be based on the treatment the participant received.
	
 Safety, Baseline and Demographic Characteristics
Safety – LA Exposed	
All participants who received at least one injection of long-acting study treatment.
 
This population will be based on the treatment the participant received.
	
 Injection Site Reactions
Pharmacokinetic	
All participants in the Safety population who received study treatment and had at least 1 non-missing PK assessment (non-quantifiable [NQ] values will be considered as non-missing values).
 
Note: PK samples that may be affected by protocol deviations will be reviewed by the study team to determine whether or not the sample will be excluded.
	
 PK Concentration and PK Parameter

Refer to [Appendix 10: List of Data Displays](#) which details the population used for each display.

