	If actual “Time of Day” for the assessment/event is not collected: For participants receiving second CAB injection: Date of First CAB Injection ≤ AE Start Date < Date of Second CAB Injection For participants not receiving second CAB injection: Date of First CAB Injection ≤ AE Start Date ≤ Date of Nominal Follow-up Week 4/Day 28 Visit [for Part 1 participants]/ Nominal Follow-up Week 12 Visit [for Part 2 participants]
Injection 2	If actual “Time of Day” for the assessment/event is collected: Date & Time of Second CAB Injection ≤ AE Start Date & Time and AE Start Date ≤ Date of Nominal Follow-up Week 4/Day 28 Visit [for Part 1 participants]/ Nominal Follow-up Week 12 Visit [for Part 2 participants] If actual “Time of Day” for the assessment/event is not collected: Date of Second CAB Injection ≤ AE Start Date ≤ Date of Nominal Follow-up Week 4/Day 28 Visit [for Part 1 participants]/ Nominal Follow-up Week 12 Visit [for Part 2 participants]
Follow-up	AE Start Date > Date of Nominal Follow-up Week 4/Day 28 Visit [for Part 1 participants]/ Nominal Follow-up Week 12 Visit [for Part 2 participants]
For Injection Site Reaction Adverse Events (Where collected on the ISR form for study treatment associated reactions, including drug related and non-drug related)	
Injection 1	If actual “Time of Day” for the assessment/event is collected: For participants receiving second CAB injection: Date & Time of First CAB Injection ≤ AE Start Date & Time < Date & Time of Second CAB Injection For participants not receiving second CAB injection: Date & Time of First CAB Injection ≤ AE Start Date & Time If actual “Time of Day” for the assessment/event is not collected: For participants receiving second CAB injection: Date of First CAB Injection ≤ AE Start Date < Date of Second CAB Injection For participants not receiving second CAB injection: Date of First CAB Injection ≤ AE Start Date

Injection 2	If actual "Time of Day" for the assessment/event is collected:
	Date & Time of Second CAB Injection ≤ AE Start Date & Time and AE Start Date
	If actual "Time of Day" for the assessment/event is not collected:
	Date of Second CAB Injection ≤ AE Start Date
For PK Data	
Study Period	Data Range
OLI	Excluding Injection 1 Day 1 Pre-dose Samples: Start Date & Time < Date & Time of First CAB Injection

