10.7.2.1. Handling of Missing and Partial Dates

Element	Reporting Detail		
General	
 Partial dates will be displayed as captured in participant listing displays. Where necessary, partial dates may be imputed for specific analysis purposes as outlined below. Imputed partial dates will not be used to derive study day, time to onset or duration (e.g., time to onset or duration of AEs), or elapsed time variables (e.g., time since diagnosis), except for crossover analysis endpoints (see Section 7.5) in which date of last contact will be used to derive duration for ongoing events. 		
Adverse Events	
 Imputations in the AEs dataset are used for slotting events to the appropriate study time periods and for sorting in data listings. Partial dates for AE recorded in the eCRF will be imputed using the following conventions: 
 
 Missing start day	 
 If study treatment start date is missing (i.e. participant did not start study treatment), then set start date = 1st of month. Else if study treatment start date is not missing: 
 If month and year of start date = month and year of study treatment start date then 
 If stop date contains a full date and stop date is earlier than study treatment start date then set start date= 1st of month. Else set start date = study treatment start date. Else set start date = 1st of month. 	
 
 	Missing start day	
 If study treatment start date is missing (i.e. participant did not start study treatment), then set start date = 1st of month. Else if study treatment start date is not missing: 
 If month and year of start date = month and year of study treatment start date then 
 If stop date contains a full date and stop date is earlier than study treatment start date then set start date= 1st of month. Else set start date = study treatment start date. Else set start date = 1st of month.

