Missing start day	
 If study treatment start date is missing (i.e. participant did not start study treatment), then set start date = 1st of month. Else if study treatment start date is not missing: 
 If month and year of start date = month and year of study treatment start date then 
 If stop date contains a full date and stop date is earlier than study treatment start date then set start date= 1st of month. Else set start date = study treatment start date. Else set start date = 1st of month. 		

Element	Reporting Detail										
	

Missing start day and month	
• If study treatment start date is missing (i.e. participant did not start study treatment), then set start date = January 1.• Else if study treatment start date is not missing:
○ If year of start date = year of study treatment start date then
▪ If stop date contains a full date and stop date is earlier than study treatment start date then set start date = January 1.▪ Else set start date = study treatment start date.○ Else set start date = January 1.	

Missing stop day	Last day of the month will be used.	

Missing stop day and month	No Imputation	

Completely missing start/end date	No imputation	

 
• Completely missing start or end dates will remain missing, with no imputation applied.	Missing start day and month	
• If study treatment start date is missing (i.e. participant did not start study treatment), then set start date = January 1.• Else if study treatment start date is not missing:
○ If year of start date = year of study treatment start date then
▪ If stop date contains a full date and stop date is earlier than study treatment start date then set start date = January 1.▪ Else set start date = study treatment start date.○ Else set start date = January 1.	Missing stop day	Last day of the month will be used.	Missing stop day and month	No Imputation	Completely missing start/end date	No imputation		

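### The SAP's missing-start-day rule ignores injection dates, so most Injection 1 site reactions with a missing day get no injection period and most Injection 2 ones are counted under Injection 1

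*SAP*

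**What the plan says.** SAP 10.7.2.1 states what AE date imputation is for: "Imputations in the AEs dataset are used for slotting events to the appropriate study time periods". For a missing start day it has one special branch, "If month and year of start date = month and year of study treatment start date then", which uses the treatment start date unless a full stop date precedes it. Otherwise the rule is "Else set start date = 1st of month". If day and month are both missing, the same logic applies to the year: the treatment start date if the years match, otherwise 1 January. No branch mentions an injection date.

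The appendix does not define the study treatment start date. Study treatment includes oral dosing, because the Safety population in SAP section 4 is "All participants who received at least one dose of study treatment (oral or injection"), so its start is naturally the first oral dose.

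SAP Table 5 (section 10.4.1) then assigns periods. ISRs have their own block with two rows only. For a participant given both injections, and with no clock time, the Injection 1 row is "Date of First CAB Injection ≤ AE Start Date < Date of Second CAB Injection"; the Injection 2 row needs a start on or after the second injection. There is no row for an earlier date. In the general AE block, anything from the first oral dose up to the first injection belongs to the oral lead-in. The programming notes for Tables 2.2 to 2.5 restrict them to the two injection periods.

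For non-ISR events after the last injection, the boundary is the nominal follow-up visit. In Part 1 the Follow-up row is "AE Start Date > Date of Nominal Follow-up Week 4/Day 28 Visit", and nothing is said about a participant without that visit.

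**The concern.** An ISR cannot start before the injection, yet the rule gives it such a date whenever the day is missing, the onset is in the injection month and the injection was not on the 1st. After Injection 1 the event then has no column. After Injection 2 it usually lands in the Injection 1 column, which can mean another dose or route. In Cohort 4 it moves from 200 mg SC to 400 mg IM gluteal, in Cohort 2 from 200 mg to 600 mg SC, and in Cohort 4b to the other topical treatment. Protocol 2.3 names ISRs as the main safety concern, and these tables are read by injection, dose and route in small arms.

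**Working it through.** The documents give no figure on this point, so there is none to reproduce.

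**Inputs**
- Oral phase (SAP 2.3): "A 28-day OLI phase, CAB 30 mg once daily (QD) with sparse PK sampling through Day 29".
- Washout (SAP 2.3): "A 7 to 14-day Washout Period (starting on Day 29"). Injection 1 is therefore 35 to 42 days after the first oral dose, or later if washout is extended.
- Injection 2 in Part 1 (Protocol 1.1): 28 ± 3 days after Injection 1, so 25 to 31 days.
- ISR onset: assumed 0 to 7 days after the injection; other ranges are shown below.

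**Step 1: can the treatment-start branch help?** No calendar month exceeds 31 days, and 35 > 31, so Injection 1 always falls in a later month than the first oral dose. Enumerating four years of oral start dates with gaps of 35 to 42 days gives 0 same-month schedules out of 11,680. Every Injection 1 event with a missing day goes to the 1st.

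**Step 2: Injection 1 ISRs, day missing.** In a month of m days, an onset lag of L days leaves m − 1 − L injection dates that are not the 1st and still have onset in the same month. These are the cases imputed before the injection. Averaging over the lags and summing over 12 months (365.25 days):

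| Onset after injection | Mean L | Share with no injection period |
|---|---|---|
| Day 0 | 0 | (365.25 − 12 × 1)/365.25 = 96.7% |
| 0–3 days | 1.5 | (365.25 − 12 × 2.5)/365.25 = 91.8% |
| 0–7 days | 3.5 | (365.25 − 12 × 4.5)/365.25 = 85.2% |

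Full enumeration gives the same values, and 53.7% for onset 0 to 27 days (counting only onsets before Injection 2). The rest stay in Injection 1, because the injection was on the 1st or the onset was in a later month. Single-injection participants (Cohorts 4h and 5) have the same 96.7% and 85.2%.

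**Step 3: Injection 2 ISRs, day missing.** The same 85.2% (onset 0 to 7 days) are dated before Injection 2. By enumeration, 83.6% fall in Injection 1, 1.6% have no period and 14.8% stay in Injection 2. With onset on the injection day the figures are 90.9%, 5.8% and 3.3%.

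**Step 4: day and month missing.** With onset 0 to 7 days, 98.8% of Injection 1 ISRs and 91.1% of Injection 2 ISRs get no injection period.

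**Step 5: the other reading.** If the treatment start date meant the Injection 1 date, all Injection 1 ISRs with a missing day would be placed correctly, but 85.2% of Injection 2 ISRs would still go to Injection 1.

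**Example.** First oral dose 1 February 2021, Injection 1 on 15 March, Injection 2 on 12 April. Onset recorded as March 2021 becomes 1 March, which meets neither ISR row. Onset recorded as April 2021 becomes 1 April and is counted under Injection 1.

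**Non-ISR events.** The same imputation puts a non-ISR AE from the Injection 1 month in the oral lead-in.

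**The case against.** The strongest objection is that the rule may seldom be used. ISRs are assessed at 1, 2, 8 and 24 hours and repeatedly to Day 22. Later cohorts stay in clinic for several days, diary cards follow each injection, and data cleaning precedes the formal analyses. That stands: partial ISR dates are probably few, and nothing in the documents gives a count. The events also remain in Listings 17 to 19.

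The treatment start date is undefined, and some period-derivation text is redacted. That stands as a caveat, but step 5 shows that neither reading places events from both injections correctly. If the general AE rows of Table 5 were applied to ISRs first, an early-dated ISR would go to the oral lead-in, still outside Tables 2.2 to 2.5.

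A reader might infer several stronger things that the documents do not support:
- That the duration tables (2.37 to 2.40) lose events because of this rule. SAP 10.7.2.1 already bars imputed dates from duration, apart from the crossover endpoints, so a partial start date gives no duration there in any period.
- That one lost ISR moves a 10-person Cohort 4h arm by 10 points. That holds only if the participant has no other dated ISR, and Protocol 2.3.1 says most participants exposed to CAB LA have ISRs.
- That the Table 5 visit boundary misplaces every AE in early leavers. After a second injection, Injection 1 events are bounded by that injection's date. Participants who stop treatment stay in follow-up, and those who leave are asked to attend a withdrawal visit. Where the visit is missing the rule is undefined; that such events would fall in Follow-up is a guess about code that is not shown.

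**Conclusion.** The rule as written gives wrong period assignments and should be changed. Most Injection 1 ISRs with a missing start day get no injection period (85% for onset 0 to 7 days, 97% on the injection day). Most Injection 2 ISRs with a missing day are counted under Injection 1 (84% for onset 0 to 7 days). Most ISRs with day and month missing also get no injection period.

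These are shares of partially dated ISRs, not of all ISRs. They assume that the treatment start date is the first oral dose, that injection dates are spread evenly over the calendar, and that onset falls in the stated window. No effect on reported ISR rates can be given without the frequency of partial dates.

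It would be tempting to say that the rule simply removes ISRs or always understates them. It does not: it lowers Injection 1 counts by omission, and it raises them with events that belong to Injection 2.

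The missing-visit gap in Table 5 is secondary. It reaches only non-ISR AEs after the last injection in participants without the nominal visit.

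**What to change.** In SAP 10.7.2.1:
- If the partial start month contains one or more CAB injections, set the start to the latest injection in that month that is not after the stop date (when a full stop date exists). If none qualifies, keep the current rule.
- For an ISR with day and month missing, use the latest injection in that year that is not after any full stop date.
- Never impute an ISR start earlier than the first injection.
- State which date the study treatment start date is.

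In Table 5, if the nominal Follow-up Week 4 (Part 1) or Week 12 (Part 2) visit is missing, close the injection period for non-ISR AEs at the last injection + 28 days (Part 1) or + 84 days (Part 2).

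The cost is a few sentences of SAP text and a few lines of dataset code, with no new data. There are two downsides. Some washout AEs in the injection month will be counted under Injection 1, which is the conservative direction. A late Injection 1 reaction with no stop date, or one after Injection 2, can be assigned to Injection 2 when its partial date covers that injection. Listing every ISR with an imputed start would let both be checked.

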10.8. Appendix 8: Values of Potential Clinical Importance

10.8.1. Laboratory Values and Site Reactions to Injections and Infusions

Laboratory values and site reactions to injections and infusions will be graded based on the Division of AIDS Table for Grading the Severity of Adult and Pediatric Adverse Events Version 2.1, July 2017, as specified in the protocol Appendix 11.7, and shown below. Only numeric portion will be used, and higher grade will be assigned if the same criteria is applied to multiple grades.

HEMATOLOGY				
	Grade 1	Grade 2	Grade 3	Grade 4
Absolute Lymphocyte Count, Low (cell/mm ³ ; cells/L) > 5 years of age (not HIV infected)	600 to < 650 0.600 × 10 ⁹ to < 0.650 × 10 ⁹	500 to < 600 0.500 × 10 ⁹ to < 0.600 × 10 ⁹	350 to < 500 0.350 × 10 ⁹ to < 0.500 × 10 ⁹	< 350 < 0.350 × 10 ⁹
Absolute Neutrophil Count, Low (cells/mm ³ ; cells/L) > 7 days of age	800 to 1,000 0.800 × 10 ⁹ to 1.000 × 10 ⁹	600 to 799 0.600 × 10 ⁹ to 0.799 × 10 ⁹	400 to 599 0.400 × 10 ⁹ to 0.599 × 10 ⁹	< 400 < 0.400 × 10 ⁹
Hemoglobin, Low (g/dL; mmol/L) ≥ 13 years of age (male only)	10.0 to 10.9 6.19 to 6.76	9.0 to < 10.0 5.57 to < 6.19	7.0 to < 9.0 4.34 to < 5.57	< 7.0 < 4.34
Hemoglobin, Low (g/dL; mmol/L) ≥ 13 years of age (female only)	9.5 to 10.4 5.88 to 6.48	8.5 to < 9.5 5.25 to < 5.88	6.5 to < 8.5 4.03 to < 5.25	< 6.5 < 4.03
Platelets, Decreased (cells/mm ³ ; cells/L)	100,000 to < 125,000 100.000 × 10 ⁹ to < 125.000 × 10 ⁹	50,000 to < 100,000 50.000 × 10 ⁹ to < 100.000 × 10 ⁹	25,000 to < 50,000 25.000 × 10 ⁹ to < 50.000 × 10 ⁹	< 25,000 < 25.000 × 10 ⁹
White Blood Cell, Decreased (cells/mm ³ ; cells/L) > 7 days of age	2,000 to 2,499 2.000 × 10 ⁹ to 2.499 × 10 ⁹	1,500 to 1,999 1.500 × 10 ⁹ to 1.999 × 10 ⁹	1,000 to 1,499 1.000 × 10 ⁹ to 1.499 × 10 ⁹	< 1,000 < 1.000 × 10 ⁹

Coagulation				
	Grade 1	Grade 2	Grade 3	Grade 4
INR, High	1.1 to < 1.5 × ULN	1.5 to < 2.0 × ULN	2.0 to < 3.0 × ULN	≥ 3.0 × ULN
PTT, High	1.1 to < 1.66 × ULN	1.66 to < 2.33 × ULN	2.33 to < 3.00 × ULN	≥ 3.00 × ULN
PT, High	1.1 to < 1.25 × ULN	1.25 to < 1.50 × ULN	1.50 to < 3.00 × ULN	≥ 3.00 × ULN

Clinical Chemistry				
	Grade 1	Grade 2	Grade 3	Grade 4
Alkaline Phosphatase, High	1.25 to < 2.5 × ULN	2.5 to < 5.0 × ULN	5.0 to < 10.0 × ULN	≥ 10.0 × ULN
Alanine Aminotransferase, High	1.25 to < 2.5 × ULN	2.5 to < 5.0 × ULN	5.0 to < 10.0 × ULN	≥ 10.0 ULN
Aspartate Aminotransferase, High	1.25 to < 2.5 × ULN	2.5 to < 5.0 × ULN	5.0 to < 10.0 × ULN	≥ 10.0 × ULN
Direct Bilirubin, High > 28 days of age	NA	NA	> ULN with other signs and symptoms of hepatotoxicity	> ULN with life-threatening consequences (e.g., signs and symptoms of liver failure)
Total Bilirubin, High > 28 days of age	1.1 to < 1.6 × ULN	1.6 to < 2.6 × ULN	2.6 to < 5.0 × ULN	≥ 5.0 × ULN
Calcium, High (mg/dL; mmol/L) ≥ 7 days of age	10.6 to < 11.5 2.65 to < 2.88	11.5 to < 12.5 2.88 to < 3.13	12.5 to < 13.5 3.13 to < 3.38	≥ 13.5 ≥ 3.38
Calcium, Low (mg/dL; mmol/L) ≥ 7 days of age	7.8 to < 8.4 1.95 to < 2.10	7.0 to < 7.8 1.75 to < 1.95	6.1 to < 7.0 1.53 to < 1.75	< 6.1 < 1.53
Creatine Kinase, High	3 to < 6 × ULN	6 to < 10 × ULN	10 to < 20 × ULN	≥ 20 × ULN
Creatinine, High Choose the method that selects for the higher grade	1.1 to 1.3 × ULN	> 1.3 to 1.8 × ULN OR Increase to 1.3 to < 1.5 × participant's baseline	> 1.8 to < 3.5 × ULN OR Increase to 1.5 to < 2.0 × participant's baseline	≥ 3.5 × ULN OR Increase of ≥ 2.0 × participant's baseline
Glucose Fasting, High (mg/dL; mmol/L)	110 to 125 6.11 to < 6.95	> 125 to 250 6.95 to < 13.89	> 250 to 500 13.89 to < 27.75	≥ 500 ≥ 27.75
Glucose, Low (mg/dL; mmol/L) ≥ 1 month of age	55 to 64 3.05 to < 3.55	40 to < 55 2.22 to < 3.05	30 to < 40 1.67 to < 2.22	< 30 < 1.67
Potassium, High (mEq/L; mmol/L)	5.6 to < 6.0 5.6 to < 6.0	6.0 to < 6.5 6.0 to < 6.5	6.5 to < 7.0 6.5 to < 7.0	≥ 7.0 ≥ 7.0
Potassium, Low (mEq/L; mmol/L)	3.0 to < 3.4 3.0 to < 3.4	2.5 to < 3.0 2.5 to < 3.0	2.0 to < 2.5 2.0 to < 2.5	< 2.0 < 2.0
Sodium, High (mEq/L; mmol/L)	146 to < 150 146 to < 150	150 to < 154 150 to < 154	154 to < 160 154 to < 160	≥ 160 ≥ 160
Sodium, Low (mEq/L; mmol/L)	130 to < 135 130 to < 135	125 to < 130 125 to < 130	121 to < 125 121 to < 125	≤ 120 ≤ 120

Site Reactions to Injections and Infusions				
	Grade 1	Grade 2	Grade 3	Grade 4
Injection Site Erythema or Redness > 15 years of age	2.5 to < 5 cm in diameter OR 6.25 to < 25 cm ² surface area	≥ 5 to < 10 cm in diameter OR ≥ 25 to < 100 cm ² surface area	≥ 10 cm in diameter OR ≥ 100 cm ² surface area	-
Injection Site Induration or Swelling > 15 years of age	2.5 to < 5 cm in diameter OR	≥ 5 to < 10 cm in diameter OR ≥ 25 to < 100	≥ 10 cm in diameter OR ≥	-

	6.25 to < 25 cm ² surface area	cm ² surface area	100 cm ² surface area	
--	--	---------------------------------	-------------------------------------	--

NA=not applicable; LLN = lower limit of normal; ULN=upper limit of normal.

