8.2.6. Assessment of Injection Site Reactions

Injection Site Reaction examination will include an assessment of pain (or tenderness), pruritis, warmth, infections, rash, erythema (or redness), swelling (or induration), and nodules (granulomas or cysts). Digital photographs will be documented on all participants who have an injection site reaction that are considered more serious by the principal investigator (PI), e.g. Grade 2 or above or if persistent beyond 2 weeks.

Injection site erythema/redness or swelling/induration will be evaluated and graded using the greatest measured surface area (as well as impact with usual social and functional activities) as per DAIDS and data regarding the size of these injection site reactions recorded at each ISR assessment. The greatest width and length of these injections site reactions should be recorded in the CRF at each ISR assessment (Cohorts 4, 5 and 6). If the grade of an ISR changes over time, each change will also be recorded in the CRF. See Section [11.7](#) The Division of AIDS Table for Grading the Severity of Adult and Pediatric Adverse Events (“DAIDS AE Grading Table”).

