4. Record the date/time of the PK blood sample draw and the date/time of the last dose of study intervention prior to PK blood sample draw on the CRF. If the date or time of the last dose is unclear, provide the participant's best approximation. If the date/time of the last dose cannot be approximated OR a PK sample cannot be collected in the time period indicated above, do not obtain a PK sample. Instructions for sample handling and shipping are in the SRM.

References

11.7. Appendix 7: Division of AIDS Table for Grading the Severity of Adult and Paediatric Adverse Events Version 2.1, March 2017

The Division of AIDS Table for Grading the Severity of Adult and Pediatric Adverse Events (“DAIDS AE Grading Table”) is a descriptive terminology which can be utilised for Adverse Event (AE) reporting. A grading (severity) scale is provided for each AE term.

The table can be found at:

<https://rsc.niaid.nih.gov/sites/default/files/daidsgradingcorrectedv21.pdf> (accessed 6 April 2020)

The severity of injection site erythema/redness and swelling/induration will be graded based on surface area (and other symptoms) according to DAIDS.

Reference

U.S. Department of Health and Human Services, National Institutes of Health, National Institute of Allergy and Infectious Diseases, Division of AIDS. Division of AIDS (DAIDS) Table for Grading the Severity of Adult and Pediatric Adverse Events, Version 2.1. [March 2017]. Available from:
<https://rsc.tech-res.com/docs/default-source/safety/daids-ac-grading-table-mar2017.pdf>

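### SAP 10.8.1 grades injection-site erythema and swelling on size only, while the protocol grades on surface area plus functional impact; the SAP does not declare the difference or say which grade feeds its tables

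*SAP*

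**What the plan says.** Protocol 8.2.6 says that erythema/redness and swelling/induration are "graded using the greatest measured surface area (as well as impact with usual social and functional activities) as per DAIDS". Protocol Appendix 7 (Section 11.7) says their severity "will be graded based on surface area (and other symptoms) according to DAIDS". Neither names diameter. Section 8.2.6 also has the site keep a running grade: "If the grade of an ISR changes over time, each change will also be recorded in the CRF".

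SAP 10.8.1 covers laboratory values and site reactions together, cites Protocol Appendix 11.7 as its source, and adds: "Only numeric portion will be used, and higher grade will be assigned if the same criteria is applied to multiple grades". The row headed "Injection Site Erythema or Redness > 15 years of age" and the matching induration row define Grade 2 as "≥ 5 to < 10 cm in diameter OR ≥ 25 to < 100" cm² of surface, and Grade 3 as "≥ 10 cm in diameter OR ≥" 100 cm². No functional criterion appears, and the Grade 4 cell holds a dash.

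SAP 2.1 reports no change from the analysis planned through protocol amendment 6. Functional impact appears in a few displays:

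- Table 2.3 (Cohorts 2, 4, 4b and 5) summarises it, but only among reactions already at Grade 2 or above.
- Table 2.5 reports it for Cohort 4h.
- Tables 2.38 and 2.40 grade on it, for Cohort 4h only.
- Listing 19 lists the impact variables for Parts 1 and 2.

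**The concern.** The SAP points to the protocol appendix as its grading source and then drops part of what that appendix prescribes. This is a stated rule that differs from the protocol, not a missing detail. Protocol 2.3 names injection-site reactions as the main safety concern, so the grade attached to each one is central to the safety report.

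Read literally, the SAP rule can move grades in two directions. A small reaction that disrupts daily life is held to its size grade. A long, narrow reaction can be promoted on its length. At stake are the reported counts at Grade 2 and Grade 3, the content of Table 2.3, the duration-at-grade summaries in Tables 2.37 and 2.39, and agreement between those tables and the grades recorded at site.

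**Working it through.** No sample-size or power figure bears on this point, and the plan gives no figure to reproduce. The check applies the printed cut-offs to example reactions.

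**Inputs.** SAP 10.8.1 gives Grades 1/2/3 from 2.5/5/10 cm in diameter, or from 6.25/25/100 cm² in area. The documents give no formula for area and no definition of diameter. I take area = length x width (L x W) and diameter = greatest length. Where a reaction meets two grades by different measures, I take the higher.

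**Structure of the cut-offs.** 2.5² = 6.25, 5² = 25 and 10² = 100. Since width cannot exceed length, L x W cannot exceed L², so the area grade can never exceed the length grade. On these readings the diameter criterion can only raise a grade.

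| Reaction (cm) | Area L x W (cm²) | Grade by area | Grade by length | SAP 10.8.1 grade |
|---|---|---|---|---|
| 3 x 3 | 9 | 1 | 1 | 1 |
| 6 x 4 | 24 | 1 | 2 | 2 |
| 10 x 2 | 20 | 1 | 3 | 3 |
| 12 x 3 | 36 | 2 | 3 | 3 |
| 10 x 10 | 100 | 3 | 3 | 3 |

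**Sensitivity to the area formula.** As an ellipse, area = π x L x W / 4. The five areas become 7.1, 18.8, 15.7, 28.3 and 78.5 cm². The area grades are unchanged except for the last, which falls to Grade 2 while its length still gives Grade 3.

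**Sensitivity to the meaning of diameter.** If diameter were the mean of length and width, the 12 x 3 cm reaction would have (12 + 3) / 2 = 7.5 cm, which is Grade 2 and agrees with its area grade. The upward shift for that example then disappears.

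**Downward direction.** The 3 x 3 cm reaction is Grade 1 under SAP 10.8.1 whatever its impact. Under Protocol 8.2.6 it would be higher if impact alone can raise the grade. The documents do not print the DAIDS functional cut-offs, so that is an assumption. It is supported by the titles of SAP Tables 2.38 and 2.40, which set a grade from DAIDS impact categories, associated Grade 3 reactions and potentially life-threatening consequences. Because Table 2.3 starts at Grade 2, a reaction held at Grade 1 would not appear there.

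**The case against.** The strongest reply is that no readable passage says the reaction tables use a grade derived by program under 10.8.1. The site grades per DAIDS and records the grade and its changes in the CRF. SAP 7.1 analyses these events under the sponsor's core data standards. If the CRF grade feeds the tables, no count changes. SAP 10.6.3 is partly redacted and may hold the derivation. This stands, and it makes the consequence conditional. It does not remove the conflict: 10.8.1 says site reactions will be graded its way, and the readable text does not say where that grade is used.

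The reply on the upward direction also stands in part. The protocol defers to DAIDS, and the SAP presents diameter as a DAIDS criterion, so the protocol may not intend area only.

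Four stronger readings are tempting and are not supported:

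- *The whole SAP ignores function.* Tables 2.3, 2.5, 2.38 and 2.40 use it, and Listing 19 carries the impact data without a grade or cohort limit. Small disabling reactions would be missing from a summary table, not from the report.
- *Every reaction under 25 cm² with functional impact stays at Grade 1.* The 6 x 4 cm and 10 x 2 cm examples reach Grades 2 and 3 on length. A 2 x 2 cm reaction (4 cm²) meets no listed grade at all.
- *Pausing decisions would be wrong.* The Protocol 7.1 rules (more than 40% of injections at Grade 2 or above; at least 20% at Grade 3 or above) are applied during the study, count all local reactions, and are not altered by the SAP. Only later agreement with reported counts is in question.
- *The misclassified share can be stated.* Any percentage would need an assumed distribution of reaction sizes and shapes, which the documents do not supply.

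**Conclusion.** The point holds as a conflict between documents with a conditional effect. SAP 10.8.1 prescribes numeric-only grading, with no Grade 4, for reactions that Protocol 8.2.6 and Appendix 7 grade on area plus functional impact or symptoms, and SAP 2.1 does not disclose it.

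The downward shift requires that the tables use the 10.8.1 grade and that impact alone can raise a DAIDS grade. The upward shift requires that the tables use the 10.8.1 grade, that diameter means greatest length, and that the protocol means area only. The examples show possible one-grade and two-grade moves, but the number of participants affected cannot be estimated. The SAP should be corrected because reaction grade is a key safety result and the remedy is cheap.

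**What to change.** In SAP 10.8.1, remove erythema/redness and induration/swelling from the numeric-only rule. In the reaction tables by grade (2.2 to 2.4, 2.37 and 2.39), use the Protocol 8.2.6 grade. That is either the CRF-recorded DAIDS grade or, where the fields exist, the higher of the surface-area grade and the functional or symptom grade, including Grade 4. State which source feeds each table, whether diameter counts and how it is measured, and how area is calculated. Keep a size-only version as supportive. Leave Tables 2.38 and 2.40 as they are, because they are deliberately graded on impact for Cohort 4h. The same edit can reconcile the DAIDS version 2.1 date, which is July 2017 in the SAP and March 2017 in the protocol.

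If size-only grading is intended, declare it in SAP 2.1 as a departure and show both gradings for every cohort with the data.

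The cost is SAP wording and some reprogramming; the impact fields are already planned for Listing 19. Field availability needs checking by cohort: Protocol 8.2.6 names only Cohorts 4, 5 and 6 for recording greatest width and length, while SAP Figure 2.1 plots surface area for Cohorts 2, 4, 4b, 4h and 5. Cohorts without size or impact fields would keep the CRF grade, with a footnote.
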